#### Design Diagram – AMPLIFY TRIAL REPLICATION

## 5. Cohort Identification

### 5.1 Cohort Summary

This study will involve a new user, parallel group, propensity score-matched, retrospective cohort study design comparing apixaban to warfarin users. The patients will be required to have continuous enrollment during a baseline period of 180 days before initiation of apixaban or warfarin (index date). We will restrict the analyses to patients with a diagnosis of proximal DVT, PE, or both.

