| • Acute symptomatic proximal deep vein thrombosis (DVT) with evidence of proximal thrombosis that involves at least the popliteal vein or a more proximal vein, demonstrated by imaging with: - compression ultrasound (CUS), including grey-scale or color-coded Doppler, OR - ascending contrast venography                                                                                                                                                                                        | Measured 180 days prior to and including day of drug initiation in any diagnosis position and in an inpatient or ED care setting

Deep vein thrombosis (DVT):
ICD-9 Dx: 451.xx, 453.xx
ICD-10 Dx: I26.xx, I80.xx, I81.xx, I82.xx, I26.xx |                                                                                                                                                                                                                                                                                  |                                                                                                                                                                                                                                                                                                                                                                                                                                                                                                                    |

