| • Acute symptomatic PE with evidence of thrombosis demonstrated by imaging as follows:
- an intraluminal filling defect in segmental or more proximal branches on spiral computed tomography (CT) scan; or
- an intraluminal filling defect or a sudden cutoff of vessels more than 2.5 mm in diameter on the pulmonary angiogram; or
- a perfusion defect of at least 75% of a segment with a local normal ventilation result (high probability) on ventilation/perfusion lung scan (VPLS) | Measured 180 days prior to and including day of drug initiation in any diagnosis position and in an inpatient or ED care setting

Pulmonary embolism (PE):
ICD-9 Dx: 415.xx
ICD-10 Dx: I26.xx                                            |                                                                                                                                                                                                                                                                                  |                                                                                                                                                                                                                                                                                                                                                                                                                                                                                                                    |

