# Appendix A

|                                             |                                                                                            |
|---------------------------------------------|--------------------------------------------------------------------------------------------|
| 453.9                                       | EMBOLISM AND THROMBOSIS OF UNSPECIFIED SITE                                                |
| ICD-10 Dx inpatient primary position |                                                                                            |
| PE                                   |                                                                                            |
| I26.0                                       | Pulmonary embolism with acute cor pulmonale                                                |
| I26.01                                      | Septic pulmonary embolism with acute cor pulmonale                                         |
| I26.02                                      | Saddle embolus of pulmonary artery with acute cor pulmonale                                |
| I26.09                                      | Other pulmonary embolism with acute cor pulmonale                                          |
| I26.9                                       | Pulmonary embolism without acute cor pulmonale                                             |
| I26.99                                      | Other pulmonary embolism without acute cor pulmonale                                       |
| DVT                                  |                                                                                            |
| I80.1                                       | Phlebitis and thrombophlebitis of femoral vein                                             |
| I80.10                                      | Phlebitis and thrombophlebitis of unspecified femoral vein                                 |
| I80.11                                      | Phlebitis and thrombophlebitis of right femoral vein                                       |
| I80.12                                      | Phlebitis and thrombophlebitis of left femoral vein                                        |
| I80.13                                      | Phlebitis and thrombophlebitis of femoral vein, bilateral                                  |

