## Appendix A

|         |                                                                                                 |
|---------|-------------------------------------------------------------------------------------------------|
| I82.441 | Acute embolism and thrombosis of right tibial vein                                              |
| I82.442 | Acute embolism and thrombosis of left tibial vein                                               |
| I82.443 | Acute embolism and thrombosis of tibial vein, bilateral                                         |
| I82.449 | Acute embolism and thrombosis of unspecified tibial vein                                        |
| I82.49  | Acute embolism and thrombosis of other specified deep vein of lower extremity                   |
| I82.491 | Acute embolism and thrombosis of other specified deep vein of right lower extremity             |
| I82.492 | Acute embolism and thrombosis of other specified deep vein of left lower extremity              |
| I82.493 | Acute embolism and thrombosis of other specified deep vein of lower extremity, bilateral        |
| I82.499 | Acute embolism and thrombosis of other specified deep vein of unspecified lower extremity       |
| I82.4Y  | Acute embolism and thrombosis of unspecified deep veins of proximal lower extremity             |
| I82.4Y1 | Acute embolism and thrombosis of unspecified deep veins of right proximal lower extremity       |
| I82.4Y2 | Acute embolism and thrombosis of unspecified deep veins of left proximal lower extremity        |
| I82.4Y3 | Acute embolism and thrombosis of unspecified deep veins of proximal lower extremity, bilateral  |
| I82.4Y9 | Acute embolism and thrombosis of unspecified deep veins of unspecified proximal lower extremity |
| I82.4Z  | Acute embolism and thrombosis of unspecified deep veins of distal lower extremity               |
| I82.4Z1 | Acute embolism and thrombosis of unspecified deep veins of right distal lower extremity         |
| I82.4Z2 | Acute embolism and thrombosis of unspecified deep veins of left distal lower extremity          |
| I82.4Z3 | Acute embolism and thrombosis of unspecified deep veins of distal lower extremity, bilateral    |
| I82.4Z9 | Acute embolism and thrombosis of unspecified deep veins of unspecified distal lower extremity   |
| I82.5   | Chronic embolism and thrombosis of deep veins of lower extremity                                |

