| I82.5Z  | Chronic embolism and thrombosis of unspecified deep veins of distal lower extremity               |
| I82.5Z1 | Chronic embolism and thrombosis of unspecified deep veins of right distal lower extremity         |
| I82.5Z2 | Chronic embolism and thrombosis of unspecified deep veins of left distal lower extremity          |
| I82.5Z3 | Chronic embolism and thrombosis of unspecified deep veins of distal lower extremity, bilateral    |
| I82.5Z9 | Chronic embolism and thrombosis of unspecified deep veins of unspecified distal lower extremity   |
| I82.6   | Acute embolism and thrombosis of veins of upper extremity                                         |
| I82.60  | Acute embolism and thrombosis of unspecified veins of upper extremity                             |
| I82.601 | Acute embolism and thrombosis of unspecified veins of right upper extremity                       |
| I82.602 | Acute embolism and thrombosis of unspecified veins of left upper extremity                        |
| I82.603 | Acute embolism and thrombosis of unspecified veins of upper extremity, bilateral                  |
| I82.609 | Acute embolism and thrombosis of unspecified veins of unspecified upper extremity                 |
| I82.62  | Acute embolism and thrombosis of deep veins of upper extremity                                    |
| I82.621 | Acute embolism and thrombosis of deep veins of right upper extremity                              |
| I82.622 | Acute embolism and thrombosis of deep veins of left upper extremity                               |
| I82.623 | Acute embolism and thrombosis of deep veins of upper extremity, bilateral                         |

[figure not shown]

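### The proximal-DVT entry criterion lists the plan's PE code on the ICD-10 side only, and its wildcards reach chronic, arm, distal and Budd-Chiari codes; the effect on the cohort depends on how the DVT and PE criteria are combined

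*Combined protocol and SAP*

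**What the plan says.** Section 5.1 defines the population: "We will restrict the analyses to patients with a diagnosis of proximal DVT, PE, or both". Appendix A also introduces the DVT and PE criteria as alternatives. The trial definition in the DVT row requires "evidence of proximal thrombosis that involves at least the popliteal vein or a more proximal vein".

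The claims implementation of that row is "ICD-9 Dx: 451.xx, 453.xx" and "ICD-10 Dx: I26.xx, I80.xx, I81.xx, I82.xx, I26.xx". The PE row uses 415.xx for ICD-9 and "ICD-10 Dx: I26.xx". Both rows use the same 180-day window, any diagnosis position, and an inpatient or emergency setting.

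The VTE code sheet in Appendix A labels the codes. I26.0 is "Pulmonary embolism with acute cor pulmonale"; I82.5 is "Chronic embolism and thrombosis of deep veins of lower extremity"; I82.6 is "Acute embolism and thrombosis of veins of upper extremity".

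The flowchart in section 5.3 does not show alternatives. It removes patients on inclusion 3a (DVT), and then removes more on inclusion 3b (PE, in one row with age).

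**The concern.** There are two separate faults in one code list.

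- **PE inside the DVT criterion, on one coding side.** I26.xx appears twice in the ICD-10 DVT list, while its ICD-9 counterpart 415.xx appears only in the PE row. If a patient must pass both steps, an ICD-9 entrant needs a vein-clot code and a PE code, but an ICD-10 entrant needs only I26.xx. The qualifying event would then change at the coding switch, and so could case mix and recurrence risk.
- **Wildcards wider than the target.** 453.xx and I82.xx take in codes that the plan itself describes as something other than acute proximal leg thrombosis. If patients may enter on DVT alone, those clots become index events.

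The index event anchors a recurrence endpoint, and the study's purpose is to reproduce a trial population closely, so either fault weakens the comparison with the trial.

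**Working it through.** **1. Code sets side by side (Appendix A)**

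| Concept | ICD-9 | ICD-10 | In DVT row? |
|---|---|---|---|
| PE | 415.xx | I26.xx | ICD-10 only |
| Chronic leg DVT | 453.5 | I82.5 | both, by wildcard |
| Arm veins | 453.82 | I82.6 | both, by wildcard |
| Distal leg DVT | 453.42 | I82.4Z | both, by wildcard |
| Budd-Chiari | 453 (as printed) | I82.0 | both, by wildcard |

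Only the PE code differs by coding side. I81.xx is in the DVT row but nowhere in the VTE sheet.

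**2. Flowchart arithmetic (section 5.3), reproduced exactly**

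- Optum: 95,887 − 82,653 = 13,234 after 3a; − 4,641 = 8,593 after 3b.
- MarketScan: 71,640 − 60,406 = 11,234; − 2,852 = 8,382.
- Medicare: 319,192 − 277,170 = 42,022; − 21,229 = 20,793.

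The 3b row removed 4,641 + 2,852 + 21,229 = 28,722 of the 66,490 who had passed 3a (43.2%). Under an either-or rule, no one who had passed 3a could be removed for lacking PE.

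**3. Flags in the assembled cohort (Appendix B, unmatched)**

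| | N | PE flag | DVT flag | No DVT flag |
|---|---|---|---|---|
| Optum | 4,255 | 4,255 | 2,253 (52.9%) | 2,002 |
| MarketScan | 6,338 | 6,331 | 3,591 (56.7%) | 2,747 |
| Medicare | 8,389 | 8,364 | 4,313 (51.4%) | 4,076 |
| Pooled | 18,982 | 18,950 (99.8%) | 10,157 (53.5%) | 8,825 |

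(The flowchart totals 19,002; the Appendix B denominators are used here.) Everyone passed the DVT step, yet 46.5% carry no DVT flag and almost all carry PE. A DVT list that accepts I26.xx would produce this pattern.

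**4. The two readings**

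| Patient | Successive (flowchart) | Either-or (text) |
|---|---|---|
| PE only, ICD-9 | fails 3a, excluded | in, by 415.xx |
| PE only, ICD-10 | passes both by I26.xx | in, by the PE row's I26.xx |
| Chronic, arm, distal or Budd-Chiari code only | fails 3b, excluded | in, labelled acute proximal DVT |

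The I26.xx error affects eligibility under the first reading only. The wildcards matter mainly under the second.

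**5. Illustrative size of the era effect, successive reading only**

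The documents give no switch date and no counts by coding era. Assume a switch on 1 October 2015, uniform entry over the section 5.2.1 windows, the same DVT share among PE patients in both eras, and a DVT flag that reflects true DVT. Every unflagged retained patient is then an ICD-10 entrant. With f the ICD-9 share of entry, PE-only patients lost = (no DVT flag) × f/(1 − f).

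There are 406 days before the switch, in windows of 2,050, 1,594 and 1,229 days (f = 0.198, 0.255, 0.330).

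- Optum: 2,002 × 406/1,644 = 494
- MarketScan: 2,747 × 406/1,188 = 939
- Medicare: 4,076 × 406/823 = 2,011
- Total: about 3,440. Halving f gives about 1,430; quartering it gives about 660.

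**6. After matching (Appendix B)**

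The DVT flag is on 1,838/3,570 (51.5%) warfarin and 1,836/3,570 (51.4%) apixaban patients, standardised difference 0.00.

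**The case against.** The strongest reply is that the written rule is either-or. Under it every PE patient qualifies through the PE row in both coding eras, so I26.xx in the DVT row is a labelling slip that changes no one's eligibility. That is correct, and it means the era effect belongs to the combination of this code list with the flowchart's logic. A reader might infer that the code list alone makes eligibility differ by era; the documents do not support that. Nor can the chronic, arm, distal and Budd-Chiari codes cause an era difference, since they sit on both coding sides.

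Four further points stand:

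- The wildcards hardly affect the cohort as built, because almost everyone has PE.
- The DVT covariate's codes, setting and window are not printed. Also, 32 patients who passed 3b lack the PE flag, so flags and criteria are not identical. The 8,825 without a DVT flag are corroboration, not a count of patients admitted by I26.xx.
- The size model is fragile. Medicare has the largest assumed ICD-9 share but the lowest DVT share; the model absorbs this only by giving each database a different DVT share among PE patients.
- Appendix A says the full ICD-10 lists are in an external folder, so the executed list may differ from the printed one.

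The reply does not remove the point. The flowchart and the 99.8% PE share indicate that the cohort was assembled by successive exclusion, and returning to the written rule makes the wildcards decisive.

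**Conclusion.** The point holds in conditional form. The DVT criterion as printed contains the PE code on one coding side and is wider than acute proximal leg thrombosis on both.

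- **Successive exclusions:** the qualifying event differs between ICD-9 and ICD-10 data. The cohort's flags are consistent with this but do not prove it.
- **Alternatives:** there is no era effect, but chronic and non-proximal clots enter as acute proximal DVT. Up to 28,722 patients removed at the 3b row, less any who failed the age criterion, would return at that stage by the DVT row. How many of them hold only off-target codes is not stated.

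The number affected by the era difference cannot be computed from the documents. Roughly 660 to 3,400 is an illustration under the stated assumptions, and the upper figure should not be read as an estimate.

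A reader might also infer confounding between arms, because the DVT share before matching is 59.0% for warfarin and 48.6% for apixaban. The documents do not support that: the shares agree after matching, and no entry dates by arm are given. What is at stake is fidelity to the trial population and consistency over calendar time.

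**What to change.** Make these changes together:

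1. Apply 3a and 3b as alternatives, as section 5.1 states. Deleting I26.xx while the steps stay successive would require DVT plus PE of everyone.
2. Remove I26.xx from the DVT row and leave PE to the PE row.
3. Replace the wildcards with acute proximal leg codes from the plan's VTE sheet, with matched scope: 453.41, 451.11 and 451.81 for ICD-9; I82.41 to I82.43, I82.4Y, and the femoral, iliac and popliteal I80 codes for ICD-10. The sheet itemises no ICD-9 popliteal phlebitis code, so state how that gap is handled.
4. Justify or remove I81.xx. It is absent from the VTE sheet and the documents do not label it.
5. State whether unspecified deep leg vein codes are in or out.
6. Confirm that the executed list matches the printed one, and print the DVT covariate's codes.
7. Rerun flowchart, matching and power, and report counts by coding era.

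The cost is a code-list edit, one rerun of cohort assembly and matching, and restated counts. The unspecified-site decision trades specificity against sample size. Section 13 shows no comparative analysis recorded, so on the documents the change can be made before treatment effects are seen. No corrected sample size or power can be given from the documents.

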# Appendix A

|                                                                                                                                                                                                     |                                                                                                                                                                                                                                                                                                                                                                                                                       |                                                                                                                                                                                       |  |
|-----------------------------------------------------------------------------------------------------------------------------------------------------------------------------------------------------|-----------------------------------------------------------------------------------------------------------------------------------------------------------------------------------------------------------------------------------------------------------------------------------------------------------------------------------------------------------------------------------------------------------------------|---------------------------------------------------------------------------------------------------------------------------------------------------------------------------------------|--|
| 
Thrombectomy, insertion of a caval filter, or use of a fibrinolytic agent to treat the current episode of venous thromboembolism (VTE).
                                                      | 
Measured 30 days prior and including the day of drug initiation in any diagnosis position in an inpatient or ED care setting
 
Thrombectomy:
CPT codes: 37184, 37185, 37186, 37187, 37188
HCPCS codes: C1757
 
Caval filter:
CPT codes: 37191, 37192, 37193
HCPCS codes: C1880
 
Fibrinolytic agent:
streptokinase, alteplase, reteplase, tenecteplase
 | 
Components will act as both exclusion criterion and censoring events
                                                                                                           |  |
| 
Active bleeding or high risk for bleeding contraindicating treatment with low-molecularweight heparin (LMWH) and a vitamin K antagonist (VKA)
                                                | 
Measured 30 days prior to and including the day of drug initiation
 
HAS-BLED score >=3
                                                                                                                                                                                                                                                                                                                | 
Major bleeding risk 5.8% per year for score 3
 
https://www.ncbi.nlm.nih.gov/pmc/articles/PMC4407886/
 |  |
| 
Subjects with cancer who will be treated for 6 months or more with LMWH therapy
                                                                                                              | 
N/A
                                                                                                                                                                                                                                                                                                                                                                                                            |                                                                                                                                                                                       |  |
| 
Subjects with contraindications according to the local prescribing information of enoxaparin or warfarin
                                                                                     | 
N/A
                                                                                                                                                                                                                                                                                                                                                                                                            |                                                                                                                                                                                       |  |
| 
Subjects with an indication, other than VTE, intended for long-term treatment with a VKA such as:
                                                                                            | 
N/A
                                                                                                                                                                                                                                                                                                                                                                                                            |                                                                                                                                                                                       |  |
| 
Mechanical valve
                                                                                                                                                                             | 
Measured 180 days prior to and including the drug initiation in any diagnosis position and in an inpatient or outpatient care setting
 
Mechanical valve
ICD-9 Dx: V43.3x
ICD-10 Dx: Z95.2x, Z95.3x, Z95.4x
ICD-9 Px: 35.0x, 35.2x, 35.3x
ICD-10 Px: O2RGxxx, O2RFxxx, O2RHxxx, O2RJxxx, O2QGxxx, O2QFxxx, O2QHxxx, O2QJxxx
                                                        |                                                                                                                                                                                       |  |
| 
Atrial fibrillation or atrial flutter with moderate to high risk of systemic thromboembolism. Subjects with atrial fibrillation that appears to be associated with acute PE may participate.
 | 
N/A
                                                                                                                                                                                                                                                                                                                                                                                                            |                                                                                                                                                                                       |  |
| 
Conditions for which serious bleeding may occur and the time of exclusion relative to the time of randomization:
 
* 6 months
                                                           |                                                                                                                                                                                                                                                                                                                                                                                                                       |                                                                                                                                                                                       |  |
| 
Intracranial bleeding
                                                                                                                                                                        | 
Measured 180 days prior to and including the day of drug initiation in any diagnosis position and in an inpatient care setting
 
Intracranial hemorrhage:
ICD-9 Dx: 430.xx, 431.xx, 432.xx
ICD-10 Dx: I60.xx, I61.xx, I62.xx
                                                                                                                                                               |                                                                                                                                                                                       |  |
| 
Intraocular bleeding
                                                                                                                                                                         | 
Measured 180 days prior to and including the day of drug initiation in any diagnosis position and in an inpatient care setting
 
Vitreous hemorrhage:
ICD-9 Dx: 379.23
ICD-10 Dx: H43.1x
 
Retinal hemorrhage:
ICD-9 Dx: 362.81
ICD-10 Dx: H35.6x, H35.73
 
Hemophthalmos
ICD-9 Dx: 360.43, 459.0x, 364.41
ICD-10 Dx: H44.8xx
                      |                                                                                                                                                                                       |  |

